Reasons for amendment

1. To provide the results of a completed Phase 1 multiple ascending dose study targeting YKP3089 doses of 400mg, 500mg and 600mg/day
2. To provide the results of a completed Phase 2 randomized, double-blind, placebo-controlled study that evaluated the efficacy and safety of YKP3089 200mg as adjunctive therapy for partial seizures.
3. To reduce the initial starting dose to 50mg and slow the titration rate to improve tolerability
4. To clarify the definition of uncontrolled partial seizures
5. To provide guidance on contraception for male subjects
6. To allow the first dose of study drug to be given at the investigator's site
7. To revise the timelines for the data monitoring committee review of data
8. To add a 50mg dosing card
9. To make minor administrative changes

Section	Old Text	Amended Text	Rationale
1.PROTOCOL SYNOPSIS Design and methodology	Subjects will first enter a titration phase lasting up to 6 weeks, during which the daily dose will be increased by 100 mg every week until the target dose is reached. Subjects having tolerability issues for the first time during Weeks 2 to 5 will have their dose reduced by 100 mg once. Subsequent to this reduction, subjects will recommence the upward titration by 50 mg increments towards their target dose until Week 6. Subjects having tolerability issues for a second time until Week 8 or having tolerability issues for the first time during Week 6 will have their dose reduced by 50 mg once and must remain at that dose for the remainder of the study.	Subjects will first enter a 6-week titration phase, during which the initial dose will be 50mg/day. The planned increase in the daily dose will be 50mg/day/week increments until 200mg is reached and after which the dose will be increased by 100mg/day/week in subjects randomized to 400mg/day. Subjects having tolerability issues for the first time during Weeks 2 to 6 will have their dose reduced by 50 or 100 mg depending on their attained dose at the time (Reduce by 50mg if taking 100mg, 150mg or 200mg; reduce by 100mg if on 300mg or 400mg). Subsequent to this reduction, subjects may at the discretion of the investigator, recommence the upward titration by 50 mg weekly increments towards their target dose until Week 6. If the subject cannot tolerate the new upward titration, the daily dose can be reduced one time by 50 mg through the end of week 8.	To improve tolerability, the dose and the titration rate is reduced
Table 1. Study Assessment Flowchart for Double-Blind Study	EEG or MRI or CT scan	EEG and MRI or CT scan	Text changed to correct typographical error
4.4.4 Clinical safety	Approximately 400 human subjects have been exposed to YKP3089 in 12 completed (11 Phase 1 and 1 proof-of-concept) and 3 ongoing clinical studies (1 Phase 2a and 2 Phase 1 studies).	Approximately 400 human subjects have been exposed to YKP3089 in 15 completed (13 Phase 1, 1 proof-of-concept and 1 Phase 2a). In a multiple ascending dose study in healthy volunteers,	Text revised to update safety results from recently completed

Section	Old Text	Amended Text	Rationale
	
In a multiple ascending dose study in healthy volunteers, when doses of 250 to 300 mg once daily were given from Day 1, somnolence, dizziness, and decreases in mean systolic blood pressure have been seen, but no serious AEs have been reported. Horizontal nystagmus, ataxia, and gait disturbance have also been observed in normal volunteers receiving 250 and 300 mg once daily. These reactions resolved after YKP3089 was discontinued at the end of the study. At 300 mg once daily, a mean shortening of the QT_{cF} interval of 10 to 15 msec was observed.
 
In an ongoing Phase 1 multiple ascending dose study that remains blinded, subjects are titrated from a starting dose of 200 mg once daily to a target dose of 400, 500, or 600 mg once daily by 100-mg increments every 5 to 7 days. To date, adverse events in the first and second cohorts are generally mild, with no discernible pattern other than drowsiness. Two subjects taking YKP3089 discontinued from the cohort targeting 500 mg once daily because of an adverse event that was probably related to YKP3089. One subject discontinued for facial swelling and rash. The other subject discontinued because of an antiepileptic hypersensitivity syndrome with symptoms consistent with DRESS syndrome. Dosing was discontinued during the blinded phase of treatment with 600 mg once daily because
	
when doses of 250 to 300 mg once daily were given from Day 1, somnolence, dizziness, and decreases in mean systolic blood pressure have been seen, but no serious AEs have been reported. Horizontal nystagmus, ataxia, and gait disturbance have also been observed in normal volunteers receiving 250 and 300 mg once daily. These reactions resolved after YKP3089 was discontinued at the end of the study. At 300 mg once daily, a mean shortening of the QT_{cF} interval of 10 to 15 msec was observed.
 
In another, now completed Phase 1 multiple ascending dose study in healthy volunteers, YKP3089C018, subjects were titrated from a starting dose of 200 mg once daily to a target dose of 400, 500, or 600 mg once daily by 100-mg increments every 5 to 7 days. Adverse events in the first and second cohorts were generally mild, with no discernible pattern other than drowsiness. All subjects following daily administration of 600 mg YKP3089 experienced multiple neurological adverse events including somnolence, ataxia, and nystagmus. Many of these AEs were probably related to the study drug and at least 2 subjects had exceeded their maximum tolerated dose. Based on the overall condition of the remaining subjects, the study was stopped. Two subjects taking YKP3089 discontinued from the cohort targeting 500 mg once daily because of an adverse event that was probably related to YKP3089. One subject discontinued for facial
	
clinical studies

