	
dose-response relationship and to compare the YKP3089 doses to each other.
 
The percentage of subjects who become seizure free (all seizure types) during the maintenance phase of the double-blind treatment period will also be analyzed.
 
Seizure frequency reductions and responder rates for partial seizure subtypes including simple partial with motor component, complex partial, and secondarily generalized tonic-clonic seizures will also be analyzed.
 
Outcome measurements will be summarized by visits or analyzed by appropriate models.
	
 • Median percent change for partial seizure subtypes (including simple partial with motor component, complex partial, and secondarily generalized tonic-clonic seizures) will be summarized. • Seizure rate over time will be analyzed using following scheme 
 o A moving average for each dose group will be computed using 4 week periods with 2 week overlap beginning from Visit 3 (V3-V5, V4-V6, V5-V6+2 weeks and so on) • For the QOLIE-31 analysis, changes from baseline (Visit 3) to the the final value (defined as the last observation obtained in the double-blind phase) (Visit 9) for each treatment group will be summarized using descriptive statistics. Differences between each treatment group and the placebo group in the change from baseline will also be summarized using descriptive statistics. The minimally important change (MIC) was defined as a change from baseline ≥ 11.8 at the End Point for the weighted overall QOLIE-31 score. The incidence of subjects meeting the MIC criteria will be summarized by treatment group. • CGIC will be summarized using descriptive 	

Section	Old Text	Amended Text	Rationale
		statistics for each treatment group and the placebo group.	

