The investigator will complete the CGIC questionnaire at Visit 9 (end of maintenance or Early Termination if applicable) to assess the subject's clinical status since starting study drug. This assessment should take into account seizure frequency and severity, the occurrence of AEs, and overall functional status of the subject ([Appendix G: Clinical Global Impression of Change \(CGIC\)](#)).

6.2.6.2 *Quality of Life in Epilepsy Questionnaire (QOLIE-31-P)*

Subjects will complete the QOLIE-31-P at Visit 3 (end of baseline) and Visit 9 (end of maintenance or Early Termination if applicable) to assess their status since starting study drug. Note, the QOLIE-31-P will only be completed by the subject; the caregiver will not be allowed to complete this questionnaire on behalf of the subject ([Appendix H: Quality of Life in Epilepsy \(QOLIE-31-P\)](#))

QOLIE-31-P *must* be completed as described in [Appendix H: Quality of Life in Epilepsy \(QOLIE-31-P\)](#). Subjects *must not* have had any simple motor or complex partial seizures within 4 hours, or generalized seizures within 24 hours before administration of the scale. If subjects have these seizure types but have fully recovered from their seizures, the outcome scale may be administered to the subjects. If subjects have not fully recovered from their seizures, the outcome scale only will be done at an unscheduled visit after recovery from seizures. If subjects experience daily seizures and the visit cannot be rescheduled, the outcome scale will be omitted. If a subject is cognitively impaired and unable to understand the scale or if a subject is unable to read, the subject will be excluded from the completion of the scale.

This questionnaire is only to be implemented in the countries where it is available and validated for the spoken language(s).

6.2.7 *Pharmacokinetic Endpoints*

Trough AED levels (oxcarbazepine [OXC], topiramate [TPM], carbamazepine [CBZ], valproate [VPA], lamotrigine [LTG], lacosamide (LMD) and levetiracetam (LEV) only) during the baseline will be compared to those during the treatment period in subjects randomized to 100, 200, or 400 mg/day YKP3089 or placebo to determine potential drug interactions.

6.3 **Safety Assessments**

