12.5 Primary Efficacy Analyses

12.5.1 Primary Efficacy Analysis in the United States and the Rest of the World:

The primary efficacy analysis of the primary endpoint will be based on the MITT population.

The testing strategy for the primary efficacy endpoint (percent change in seizure frequency) is to compare each of the YKP3089 dosage groups with the placebo group. Due to multiple treatment comparisons, a step-down procedure will be used to ensure the overall type I error rate is controlled at the 5% level. Each of the YKP3089 dosage groups will be compared with the placebo group according to the following hierarchy:

1. 200-mg dosage group versus placebo group
2. 400-mg dosage group versus placebo group
3. 100-mg dosage group versus placebo group

The 200-mg dosage group will be compared with the placebo group at a 2-sided 0.05 level as the first step. If no statistically significant difference is detected between the 200-mg dosage group and the placebo group, the procedure will stop and it will be concluded that none of the YKP3089 dosages are efficacious. If a statistically significant difference is detected between the 200-mg dosage group and the placebo group in favor of the 200-mg dosage group, the procedure will proceed to the next step to compare the 400-mg dosage group with the placebo group at a 2-sided 0.05 level. If a statistically significant difference is detected between the 400-mg dosage group and the placebo group in favor of the 400-mg dosage group, the procedure will proceed to the next step to compare the 100-mg dosage group with the placebo group at a 2-sided 0.05 level.

An analysis of covariance (ANCOVA) model will be fit to the ranked values of the primary efficacy endpoint. The ANCOVA will have terms for ranked baseline seizure rate and randomized treatment group. Ties will be handled using the default option in SAS

It should be noted that the primary efficacy analysis uses a non-parametric approach. Because of this, effect sizes are not estimated and tested directly, since testing is made on the rank of the primary efficacy value. However, summary tables for the actual (not the ranked) primary efficacy endpoint will be presented.

Descriptive results of the primary efficacy end point will be provided for the subjects who were titrated under the original protocol.

12.5.2 *Primary Efficacy Analyses in the countries of Europe, Australia, New Zealand, and South Africa*

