- For the QOLIE-31 analysis, changes from baseline (Visit 3) to the the final value (defined as the last observation obtained in the double-blind phase) (Visit 9) for each treatment group will be summarized using descriptive statistics. Differences between each treatment group and the placebo group in the change from baseline will also be

summarized using descriptive statistics. The minimally important change (MIC) was defined as a change from baseline ≥ 11.8 at the End Point for the weighted overall QOLIE-31 score. The incidence of subjects meeting the MIC criteria will be summarized by treatment group.

- CGIC will be summarized using descriptive statistics for each treatment group and the placebo group.

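### The QOLIE-31 comparison with placebo is an unadjusted difference in change scores; adding the Visit 3 score as a covariate would give a more precise estimate at negligible cost

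*Protocol*

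**What the plan says.** Protocol Section 6.2.6.2 has subjects complete the QOLIE-31-P at Visit 3 and again at Visit 9 or early termination. It limits the questionnaire to countries with a validated version. It also excludes subjects who cannot understand or read it, and omits it for some subjects with daily seizures.

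Section 12.7 takes the change from Visit 3 to the last double-blind value and summarizes it by group. It then adds: "Differences between each treatment group and the placebo group in the change from baseline will also be summarized using descriptive statistics". It also sets a threshold, "The minimally important change (MIC) was defined as a change from baseline ≥ 11.8 at the End Point", for the weighted overall score, and says "The incidence of subjects meeting the MIC criteria will be summarized by treatment group". The amended text of 12.7 in the Amendment 2 table is the same, so this is current wording.

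No model, covariate, interval or test is given for QOLIE-31. The descriptive statistics listed in Section 12.2 (n, mean, median, SD, minimum, maximum) do not include a measure of precision for a between-group difference.

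The seizure-frequency analysis is handled differently. Section 12.5.1 states: "The ANCOVA will have terms for ranked baseline seizure rate and randomized treatment group". Section 12.6.1 uses the same covariate for the maintenance-phase change.

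**The concern.** Every subject who contributes a change score has a Visit 3 score, but the plan uses that score only by subtracting it in full. Scores at two visits are imperfectly correlated, so full subtraction over-corrects. If one arm happens to start higher, regression to the mean makes its average change look worse, and the raw difference reports part of that as a difference between treatments.

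At stake are the size and precision of the quality-of-life contrasts for the three doses against placebo. The restrictions in Section 6.2.6.2 mean that fewer than all randomized subjects will contribute, and smaller arms make a given chance imbalance more likely.

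**Working it through.** **The plan's own figure.** No sample size or power is stated for QOLIE-31. The only such figure is in Section 12.1 for the seizure endpoint: 100 per group, difference 16%, SD 40%, two-sided 0.05, 80% power. It reproduces: n = 2 × (1.960 + 0.842)² × (40/16)² = 2 × 7.849 × 6.25 = 98.1, so 99 per arm. Power at 100 per arm is 80.7%. It says nothing about QOLIE-31 precision.

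**Assumptions for QOLIE-31.** The documents give neither an SD nor a correlation. Let s be the SD at both visits, r the correlation between them, and n the number per arm.

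- Variance of the change-score difference: 2s²(1-r)(2/n).
- Variance of the ANCOVA difference: s²(1-r²)(2/n).
- Ratio, ANCOVA to change score: (1-r²)/[2(1-r)] = (1+r)/2.
- Given a chance baseline difference d between arms, the change-score difference is shifted by -(1-r)d. The ANCOVA difference is shifted by about 0.

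| r (assumed) | Variance ratio | SE ratio | Shift in raw difference per 1-point imbalance |
|---|---|---|---|
| 0.3 | 0.65 | 0.81 | -0.7 |
| 0.5 | 0.75 | 0.87 | -0.5 |
| 0.7 | 0.85 | 0.92 | -0.3 |
| 0.9 | 0.95 | 0.97 | -0.1 |

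**Simulation check** (20,000 runs per setting). At 100 per arm the variance ratios were 0.752, 0.862 and 0.953 for r of 0.5, 0.7 and 0.9. The slope of the estimate on baseline imbalance was -0.50, -0.29 and -0.10 for change scores, and within 0.01 of zero for ANCOVA.

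**Unequal variances.** With SDs s₀ at Visit 3 and s₁ at Visit 9, the two variances, before the factor 2/n, are s₀² + s₁² - 2r·s₀·s₁ and s₁²(1-r²). Their difference is (s₀ - r·s₁)², which is never negative. In large samples the direction of the gain therefore does not rest on equal SDs; its size does.

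**Cost of estimating the slope.** In a two-arm fit the variance is inflated by about 1/(2n-4): 1/196 = 0.5% at 100 per arm, 1/96 = 1.0% at 50 and 1/46 = 2.2% at 25. Setting (1+r)/2 times this inflation equal to 1 gives break-even correlations of about 0.99, 0.98 and 0.96.

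**Illustration in points** (assumed s = 16; SEs and shifts scale in proportion to s).

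- 100 per arm, r = 0.5: SE 16√(1.0 × 0.02) = 2.26 for change scores, 16√(0.75 × 0.02) = 1.96 for ANCOVA.
- 100 per arm, r = 0.7: 16√(0.6 × 0.02) = 1.75 against 16√(0.51 × 0.02) = 1.62.
- 100 per arm, r = 0.9: 16√(0.2 × 0.02) = 1.01 against 16√(0.19 × 0.02) = 0.99.
- 60 per arm (assumed reduced sample), r = 0.7: 2.26 against 2.09.
- SE of the baseline difference: 16√(2/n) = 2.26 at 100 per arm and 2.92 at 60.
- At r = 0.7, a one-SE imbalance with 100 per arm shifts the raw difference by 0.3 × 2.26 = 0.7 points. A two-SE imbalance with 60 per arm shifts it by 0.3 × 2 × 2.92 = 1.8 points.

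**The case against.** **No trial conclusion depends on this.** QOLIE-31 is an additional secondary outcome outside the step-down hierarchy, with no test, interval or alpha attached. This stands, and it keeps the point minor.

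**The gain is small and cannot be sized from the documents.** It is about 5% of variance at r = 0.9. In the illustration, shifts of 0.7 to 1.8 points are 6% to 15% of the protocol's 11.8-point threshold, and the upper end needs a two-SE imbalance. This stands as to size, though the direction holds at any realistic correlation.

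**The governing document may be elsewhere.** Section 12.2 defers full detail to an SAP. The SAP supplied covers only the open-label extension, plans no QOLIE-31 analysis and refers to a separate double-blind SAP. It does list the minimally-important-change abbreviation and a QOLIE-31-P scoring reference, so the double-blind SAP may well treat this outcome. Whether it adjusts for baseline cannot be checked, so the point is limited to the protocol text.

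**Stronger readings that the documents do not support.**

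- A reader might infer that the plan ignores the Visit 3 score. It does not; it subtracts it with coefficient 1.
- A reader might infer that adjustment is free, or better at every correlation below 1. In finite samples there is a small cost, and the change score wins very close to r = 1.
- A reader might take QOLIE-31 as the only patient-reported comparison with placebo. The seizure endpoints also come from subjects' own diaries.
- A reader might conclude that the planned contrast is biased. Over repeated randomizations it is not; the shift is conditional on the imbalance that happens to occur.

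**Conclusion.** The point holds as a minor improvement. As written, Section 12.7 plans the less precise of two simple estimators, and the one that moves with chance baseline imbalance. With equal SDs at the two visits, ANCOVA lowers the variance by about 25%, 15% and 5% for assumed r of 0.5, 0.7 and 0.9, less 0.5% to 2% for estimating the slope at 100 to 25 per arm. It removes the linear dependence on baseline imbalance, which otherwise enters at -(1-r) per point. The figures in points rest on an assumed SD of 16 and assumed correlations and arm sizes. No primary or step-down result, sample size or error rate is affected.

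**What to change.** Keep the raw summaries in Protocol Section 12.7, including the raw differences and the threshold incidence, and add:

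> The difference between each dosage group and placebo will also be estimated by ANCOVA of the change to the final double-blind score, with the Visit 3 score and randomized treatment group as terms, and reported as an adjusted mean difference with 95% CI, without a formal claim.

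Use the same analysis population as the raw QOLIE-31 summary. Section 12.7 leaves this as MITT or MITT-M, so the choice should be stated once for both. If the double-blind SAP already specifies an adjusted model, align the protocol sentence with it instead.

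The cost is one sentence and one standard model, the single degree of freedom already sized, and an assumed linear relation between the two scores. No new data are needed, and no further subjects are lost, because a change score already requires the Visit 3 value.

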
Section	Old Text	Amended Text	Rationale
	sudden unexpected death in epilepsy (SUDEP) and one case of suicide. They were considered remotely related or unrelated to study drug.	
active and 4% of subjects in the placebo-group dropped out because of adverse events. Two-thirds of subjects completed the study at the target dose of 200mg/day. The most common central nervous system adverse events in the YKP3089 group were somnolence, dizziness, fatigue, and gait disorder
 
Two suspected unexpected serious adverse reaction (SUSAR) occurred in YKP3089 treated subjects: an early manifestation of a drug hypersensitivity reaction characterized by flushed erythema of palms and soles with mild itching of ears and a status epilepticus during tapering. During the open-label extension, 2 notable serious adverse events occurred in YKP3089 treated subjects: one case of sudden unexpected death in epilepsy (SUDEP) and one case of suicide. They were considered remotely related or unrelated to study drug.
	
4.5.1 Double-Blind Dose Selection	The primary objective of this study is to determine the effective dose range of YKP3089 as adjunctive therapy for the treatment of partial seizures. According to a blinded review of an ongoing Phase 2a double-blind, randomized, placebo-controlled trial involving subjects with partial epilepsy, few subjects dropped out and 2 serious adverse events were related to YKP3089. Some subjects did not reach the maximum target dose of 200 mg. However, a daily dose of up to 500 mg was generally well tolerated by healthy volunteers in a multiple ascending dose extension	The primary objective of this study is to determine the effective dose range of YKP3089 as adjunctive therapy for the treatment of partial seizures. During the initial design of this protocol, a blinded review of the ongoing Phase 2a randomized, double-blind, placebo-controlled study YKP3089C013, revealed that few subjects dropped out and that only the two previously described serious adverse events were related to YKP3089. Some subjects did not reach the maximum target dose of 200 mg. In the multiple ascending dose study, YKP3089C018, a daily dose of up to 500 mg was	Text added to provide rationale for lower initial dose and slower titration rate

Section	Old Text	Amended Text	Rationale
	
trial.
 
In the open-label extension portion of the Phase 2a study, some subjects reportedly began to have clinically significant improvement in their seizure frequency only when they started taking a daily dose of 100 to 200 mg. A dose range of 200 to 400 mg/day should therefore be broad enough to identify efficacious doses. A 100-mg daily dose was chosen to determine the minimum effective dose.
 
Although a dose of 500 mg once daily has generally been well tolerated by healthy volunteers, the maximum dose in this study will be 400 mg once daily, to account for potential adverse pharmacodynamic interaction with the concomitant antiepileptic drugs.
 
The Phase 2a study titrated the daily dose upward by 50 mg every 2 weeks. However, the healthy volunteers in the ongoing multiple ascending dose study started with a daily dose of 200 mg, titrated upward by 100 mg every 5 to 7 days, and are tolerating the faster titration rate. Therefore, this study will begin with a daily dose of 100 mg, followed by weekly increments of 100 mg in the daily dose, to a target dose of up to 400 mg once daily.
	
generally well tolerated by healthy volunteers.
 
In the open-label extension portion of the Phase 2a study, some subjects reportedly began to have clinically significant improvement in their seizure frequency only when they started taking a daily dose of 100 to 200 mg. It was concluded that a dose range of 200 to 400 mg/day should therefore be broad enough to identify efficacious doses. A 100-mg daily dose was chosen to determine the minimum effective dose. Although a dose of 500 mg once daily has generally been well tolerated by healthy volunteers, the maximum dose chosen for the study was 400 mg once daily, to account for potential adverse pharmacodynamic interaction with the concomitant antiepileptic drugs.
 
Although the Phase 2a study titrated the daily dose upward by 50 mg every 2 weeks the healthy volunteers in the recently completed multiple ascending dose study initiated therapy with a daily dose of 200 mg, titrated upward by 100 mg every 5 to 7 days to 400 and 500mg/day, and generally well tolerated the faster titration rate. Therefore, it was initially decided that in the current study subjects would begin with a daily dose of 100 mg, followed by weekly increments of 100 mg in the daily dose, to the target dose.
 
Recently, a blinded review of the tolerability profile in the
	

